#### 11.2.3.2 Evaluation of Non-Target Lesions

Non-target lesions. All other lesions (or sites of disease) including any measurable lesions over and above the 5 target lesions should be identified as **non-target lesions** and should also be recorded at baseline. Measurements of these lesions are not required, but the presence, absence, or in rare cases unequivocal progression of each should be noted throughout follow up.

Complete Response (CR): Disappearance of all non-target lesions and normalization of tumor marker level. All lymph nodes must be non-pathological in size (<10 mm short axis).

Note: If tumor markers are initially above the upper normal limit, they must normalize for a patient to be considered in complete clinical response.

**Non-CR/Non-PD:** Persistence of one or more non-target lesion(s) and/or maintenance of tumor marker level above the normal limits.

**Progressive Disease (PD):** Appearance of one or more new lesions and/or *unequivocal progression* of existing non-target lesions. *Unequivocal progression* should not normally trump target lesion status. It must be representative of overall disease status change, not a single lesion increase.

Although a clear progression of “non-target” lesions only is exceptional, the opinion of the treating physician should prevail in such circumstances, and the progression status should be confirmed at a later time by the review panel (or Principal Investigator).

#### 11.2.3.3 Evaluation of New Lesions

The finding of a new lesion should be unequivocal (i.e. not due to difference in scanning technique, imaging modality, or findings thought to represent something other than tumor (for example, some ‘new’ bone lesions may be simply healing or flare of pre-existing lesions). However, a lesion identified on a follow-up scan in an anatomical location that was not scanned at baseline is considered new and will indicate PD. If a new lesion is equivocal (because of small size etc.), follow-up evaluation will clarify if it truly represents new disease and if PD is confirmed, progression should be declared using the date of the initial scan on which the lesion was discovered.

#### 11.2.3.4 Need for confirmatory testing

RECIST criteria specify the need for confirmation of response a minimum of 4 weeks from the disease evaluation that first demonstrated a response. Responses will be reported as confirmed or unconfirmed based upon the results of this restaging.

#### 11.2.3.5 Evaluation of Best Overall Response

The best overall response is the best response recorded from the start of the treatment until disease progression/recurrence (taking as reference for progressive disease the smallest measurements recorded since the treatment started). The patient's best response assignment will depend on the achievement of both measurement and confirmation criteria.

## Overall Response Criteria

Target Lesions	Non-Target Lesions	New Lesions*	Overall Response	Best Overall Response when Confirmation is Required
CR	CR	No	CR	≥4 wks Confirmation
CR	Non-CR/Non-PD	No	PR	≥4 wks Confirmation
CR	Not evaluated	No	PR	
PR	Non-CR/Non-PD/not evaluated	No	PR	
SD	Non-CR/Non-PD/not evaluated	No	SD	Documented at least once ≥4 wks from baseline
PD	Any	Yes or No	PD	no prior SD, PR or CR
Any	PD**	Yes or No	PD	
Any	Any	Yes	PD	

\* See RECIST 1.1 manuscript for further details on what is evidence of a new lesion.  
 \*\* In exceptional circumstances, unequivocal progression in non-target lesions may be accepted as disease progression.

Note: Participants with a global deterioration of health status requiring discontinuation of treatment without objective evidence of disease progression at that time should be reported as “*symptomatic deterioration*.” Every effort should be made to document the objective progression even after discontinuation of treatment.

### 11.3 Response Review

Patients with confirmed objective response (partial response or better) will have de-identified imaging studies submitted to the Study Coordinator for central confirmation of response. Imaging studies to be submitted include baseline scans, initial scans documenting response, and second set of scans confirming response. When relevant to the patient’s response assessment, de-identified copies of bone marrow pathology reports and tumor marker lab reports will be submitted as well.

## 12 DATA REPORTING / REGULATORY REQUIREMENTS

Adverse event lists, guidelines, and instructions for AE reporting can be found in Section 7.0.

### 12.1 Data Reporting

#### 12.1.1 Method for Data Submission

All sites will submit data using the electronic data capture system, InForm.

The DFCI Office of Data Quality (ODQ) will perform quality checks on the data for this study.

#### 12.1.2 Timelines for Data Submission

All investigative sites are expected to submit data in InForm according to the following timelines.

Form	Submission Timeline
Eligibility Checklist	Complete prior to registration
On Study Form	Within 14 days of registration
Toxicity Log (Baseline Adverse events)	Within 14 days of registration
Baseline Disease Assessment Form	Within 14 days of registration
Reporting Period Forms	Cycle 1: Within 5 business days of the last day of the cycle Other Cycles: Within 10 days of the last day of the cycle
Toxicity Log	Cycle 1: Within 5 business days of the last day of the cycle Other Cycles: Within 10 days of the last day of the cycle
Response Assessment Form	Within 14 days of the completion of disease evaluation
Off Protocol Therapy Form	Within 14 days of completing treatment
Follow-up Form	Within 14 days of the protocol defined follow up visit date and every 3 months once off therapy until 1 year after the last enrolled patient receives their final dose of protocol therapy
Off Study Form	Within 14 days of being taken off study for any reason
Outcome Form	Within 14 days of being taken off study for any reason

#### 12.2 Data Safety Monitoring

The DF/HCC Data and Safety Monitoring Committee (DSMC) will review and monitor toxicity and accrual data from this study. The committee is composed of clinical specialists with experience in oncology and who have no direct relationship with the study. Information that raises any questions about participant safety will be addressed with the Overall PI and study team.

The DSMC will review this protocol up to four times a year or more often if required to review toxicity and accrual data. Information to be provided to the committee may include: up-to-date participant accrual; current dose level information; DLT information; all grade 2 or higher unexpected adverse events that have been reported; summary of all deaths occurring within 30 days of intervention; any response information; audit results; and a summary provided by the study team. Other information (e.g. scans, laboratory values) will be provided upon request.

## 13 STATISTICAL CONSIDERATIONS

This is a prospective, open-label, non-randomized, single arm two cohort Phase 2 study to test for preliminary evidence of efficacy of the combination of palbociclib and ganitumab. The study will be powered to evaluate the efficacy of this combination separately within two different cohorts:

- A. Cohort A - relapsed or refractory Ewing sarcoma; and,
- B. Cohort B - SDH-deficient GIST.

The cohort of patients with SDH-deficient GIST was added in an amendment developed in December 2020. The toxicity of this combination will be monitored with early stopping rules separately in each cohort.

### 13.1 Study Design/Endpoints

#### 13.1.1 Study Design

The efficacy of the combination of palbociclib and ganitumab will be assessed separately within each cohort, using a one-stage design for Cohort A, and a two-stage design for Cohort B. The primary endpoint is a patient's objective overall response as defined in Section 11. A "responder" is defined as a patient having a confirmed overall response of  $\geq$  PR.

### 13.2 Sample Size, Accrual Rate and Study Duration

A total of 15 response evaluable patients with Ewing sarcoma (Cohort A) and 12 response evaluable patients with SDH-deficient GIST (Cohort B) will be required to address the primary objective. Patients who are not eligible and/or evaluable for response will be replaced.

Therefore, given potentially inevaluable patients a maximum of 33 patients with Ewing sarcoma or SDH-deficient GIST are expected to enroll.

Study Duration: We anticipate that 1-2 patients with Ewing sarcoma and 1-2 patient per GIST per month will be available for enrollment. Enrollment of the maximum sample size of 33 patients with Ewing sarcoma and GIST will require approximately 18-24 months.

### 13.3 Analysis of Primary Endpoints

#### 13.3.1 Evaluability

To be evaluable for the analysis of the primary endpoint (objective response) patients must have received at least one dose of palbociclib or ganitumab. Additionally, patients must either have evidence of clinical progression or have had at least one follow-up disease evaluation of their RECIST measurable disease after initiation of protocol therapy to be evaluable for response. Patients who receive non-protocol anti-cancer therapy during the response evaluation period after the patient is first considered as having a partial response, but prior to confirmation of this status by repeat tumor imaging and before progressive disease is noted, will be considered evaluable. Should dose de-escalation rules be met as per section 5.4.2 for either cohort, all

patients prior to de-escalation and following de-escalation will be analyzed as a single cohort within either Cohort A or Cohort B for the primary efficacy endpoint.

### 13.3.2 Response endpoint

Each patient will be classified as a responder or non-responder. Responders are defined as evaluable patients with either a complete or partial objective response, according to RECIST version 1.1.

Cohort A: Among patients with Ewing sarcoma, the response rate will be reported as the proportion of responders, among response evaluable patients. The null hypothesis that the true response rate is 10% will be tested against a one-sided alternative. This design requires 15 evaluable patients to determine whether the proportion responding is less than or equal to 10% (the estimated null response rate with IGF-1R inhibition as monotherapy) or greater than or equal to 40%. If the number of responses is 4 or more, the hypothesis that the true response rate is less than or equal to 10% will be rejected with a type 1 error rate of 0.056, and we will conclude that the combination therapy is worthy of further study in this cohort. If the number of responses is 3 or fewer, then the hypothesis that the response rate is greater than or equal to 40% will be rejected with power of 91%. A two-sided exact 95% confidence interval will be placed on the proportion of responders.

Cohort B: Among patients with SDH-deficient GIST, the response rate will be reported as the proportion of patients with complete or partial response, among response evaluable patients. The null hypothesis that the true response rate is 4% will be tested against a one-sided alternative of a 32% response rate. This design will be conducted in two stages.

In stage 1, 7 evaluable patients will be enrolled. If 0 of 7 evaluable patients are responders, there is insufficient evidence of efficacy to continue enrollment to the cohort. If  $\geq 1$  patients are responders, continue to stage 2.

In stage 2, 5 additional evaluable patients will be enrolled for a total of 12. If  $\geq 2$  of 12 evaluable patients are responders, there is sufficient evidence for further study of the combination therapy in this cohort. If  $< 2$  patients are responders, there is insufficient evidence to support further study of the combination therapy in this cohort.

The two-stage design has the following operating characteristics. If the number of responders is  $\geq 2$ , the hypothesis that the true response rate is less than or equal to 4% will be rejected with a type 1 error rate of 0.07. If the number of responses is  $< 2$ , then the hypothesis that the response rate is greater than or equal to 32% will be rejected with power of 90%.

A two-sided 95% confidence interval will be placed on the proportion of responders.

### 13.3.3 Toxicity endpoint

All toxicities observed will be summarized in terms of type (organ affected or laboratory

determination), severity (by NCI CTCAE), and attribution. Tables will be created to summarize these toxicities by cohort and by cycle.

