### 1.2 Primary Objectives

- 1.2.1 To estimate the objective radiographic response rate to the combination of palbociclib and ganitumab in a cohort of patients with relapsed or refractory Ewing sarcoma or in a separate cohort of patients with SDH-deficient GIST.
- 1.2.2 To describe the toxicity of the combination of palbociclib and ganitumab in patients with relapsed or refractory Ewing sarcoma, as well as in a separate cohort of patients with SDH-deficient GIST.

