## 2.2.2 Palbociclib: Small molecule CDK4/6 inhibitor

### 2.2.2.1 CDK4/6 activity has been implicated in Ewing sarcoma

### 2.2.2.2 Clinical experience with palbociclib

Palbociclib is an FDA-approved oral CDK4/6 inhibitor indicated for the treatment of adults with

hormone receptor-positive, HER2 negative advanced breast cancer. The approved dose is 125 mg by mouth daily for 21 days followed by 7 days of rest in 28-day cycles. This dose is tolerable when given in combination with fulvestrant or an aromatase inhibitor. The most common adverse events include neutropenia, infection, leukopenia, fatigue, nausea, stomatitis, anemia, alopecia, diarrhea, thrombocytopenia, rash, vomiting, decreased appetite, asthenia, and fever (FDA Package Insert). The most common grade 3 adverse events are neutropenia and infection.

Palbociclib has been studied in an unpublished Pediatric Brain Tumor Consortium trial, with a defined maximum tolerated dose of 75 mg/m^2/dose in that population. The ongoing Pediatric MATCH subprotocol investigating palbociclib utilizes a dose of 75 mg/m^2/dose to a maximum of 125 mg/dose. In this trial focused on adolescents and adults, flat dosing of 125 mg/dose was utilized initially, consistent with FDA draft guidance for adolescents > 40 kg. Given that two initial patients in Cohort A treated with palbociclib 125 mg dosing experienced first cycle DLTs, a contingency dosing strategy was enacted on 1/8/2020 and subsequent patients in Cohort A have started treatment with 100 mg dosing on days 1-21 of a 28-day cycle. Patients with SDH-deficient GIST do not receive upfront chemotherapy in most cases and never with the intensity given to patients with Ewing sarcoma. As such, hematologic toxicity is unlikely to be overlapping between Cohorts. Patients in Cohort B will thus start treatment at a palbociclib dose of 125 mg orally on days 1-21.

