#### 5.4.2 Dose de-escalation rules

If at any time, safety stopping rules are met as outlined in section 13.4, enrollment will be paused and one of two contingency dosing strategies for subsequent patients will be considered based upon the nature of the observed dose-limiting toxicities. The choice of contingency dose strategy will be made by the study committee in consultation with Pfizer and ImmunityBio.

Upon initial activation of this study, two of the first three enrolled patients in Cohort A experienced cycle 1 DLTs. This met stopping criteria for our interim monitoring rule and Contingency A was enacted on 1/8/2020. Should the new stopping rule as outlined in section 13.4 be met, Contingency B or C as outlined below will be considered for Cohort A. Cohort B has not yet met any stopping critiera.

- Contingency A: Palbociclib 100 mg daily on days 1-21 and ganitumab 18 mg/kg on days 1 and 15
- Contingency B: Palbociclib 75 mg daily on days 1-21 and ganitumab 18 mg/kg on days 1 and 15

- Contingency C: Palbociclib 75 mg daily on days 1-21 and ganitumab 12 mg/kg on days 1 and 15

If a contingency dosing strategy is implemented, the same monitoring rule will apply (starting anew with next enrollment). If criteria are met again for the toxicity monitoring rule, the protocol will be flagged for amendment. Any toxic death will be cause for review by the DSMB and the study committee for consideration of protocol amendment.

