#### **13.4.1 Cohort A toxicity monitoring plan**

For Cohort A, the original two-stage toxicity monitoring rule was triggered with 2 DLTs out of the first 3 evaluable patients. A new one-stage design has been developed for the remaining 12 patients, all of whom will be treated at a lower dose level than the first 3 patients (contingency A, see Section 5.4.2).

Enroll up to 12 toxicity evaluable patients. If at any time 3 or more patients have a first cycle DLT, enrollment will be paused, the trial will be reviewed by the study committee and the DSMC, and a lower dose level will be considered as outlined in Section 5.4.2. If fewer than 3 of 12 patients have a first cycle DLT, the dose level will be considered sufficiently safe for further study. This rule has the following operating characteristics. The null hypothesis is that the proportion of patients with a Cycle 1 DLT is  $\geq 39\%$  versus the alternative that the proportion with a Cycle 1 DLT is  $\leq 9\%$ . The power is 91.3% and the type 1 error is 9.5%.

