#### **13.4.2 Cohort B toxicity monitoring plan**

For Cohort B, we will utilize the following one-stage toxicity monitoring rule:

Enroll up to 12 toxicity evaluable patients. If at any time 3 or more patients have a first cycle DLT, enrollment will be paused, the trial will be reviewed by the study committee and the DSMC, and a lower dose level will be considered as outlined in Section 5.4.2. If fewer than 3 of 12 patients have a first cycle DLT, the dose level will be considered sufficiently safe for further study. This rule has the following operating characteristics. The null hypothesis is that the

proportion of patients with a Cycle 1 DLT is  $\geq 39\%$  versus the alternative that the proportion with a Cycle 1 DLT is  $\leq 9\%$ . The power is 91.3% and the type 1 error is 9.5%.

The number and proportion of toxicities will be tabulated within each cohort, by type, grade, and attribution. A given toxicity will be counted only once in a given patient, at the highest grade observed.

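### The toxicity tables in Section 13.3.3 have no dose split, so Cohort A's tables combine patients started on palbociclib 125 mg with those started on 100 mg

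*Combined protocol and SAP*

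**What the plan says.** Section 1.2 makes toxicity a primary objective: "To describe the toxicity of the combination of palbociclib and ganitumab in patients with relapsed or refractory Ewing sarcoma", with the same aim for the SDH-deficient GIST cohort.

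Section 13.3.3 plans summaries by type, severity and attribution, and then: "Tables will be created to summarize these toxicities by cohort and by cycle". Section 13.4 repeats the type, grade and attribution breakdown, and Section 13.4.2 has "The number and proportion of toxicities will be tabulated within each cohort, by type, grade, and attribution". Dose level appears in none of these.

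Cohort A has two starting doses. Section 5.4.2 records that "two of the first three enrolled patients in Cohort A experienced cycle 1 DLTs" and that this met the stopping criteria. Section 2.2.2.2 gives the starting dose of those patients as 125 mg and says that "subsequent patients in Cohort A have started treatment with 100 mg dosing on days 1-21 of a 28-day cycle". Section 5.4.2 also lists two further contingency levels for Cohort A.

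Two other places handle dose level explicitly:
- Section 13.4.1 sets a new DLT rule for the remaining 12 Cohort A patients, "all of whom will be treated at a lower dose level than the first 3 patients".
- Section 13.3.1 says that "patients prior to de-escalation and following de-escalation will be analyzed as a single cohort", but only for the primary efficacy endpoint.

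**The concern.** Elsewhere the protocol treats dose level as decisive for toxicity. The starting dose was lowered because of toxicity, the DLT count restarts at each contingency dose, and the conclusion in 13.4.1 is about the dose level. The final descriptive tables drop that distinction. Neither type, severity, attribution, cohort nor cycle separates a 125 mg start from a 100 mg start, so Cohort A's column mixes the two by default.

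The reader of those tables will want the toxicity profile at the dose given to most of the cohort, over up to 12 cycles. A mixed column can misstate it and can hide any dependence on dose. It also blurs comparison with Cohort B, which starts at 125 mg in a population whose hematologic toxicity the protocol expects to differ.

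**Working it through.** **Inputs**
- 125 mg start, Cohort A: 3 patients, 2 with a cycle 1 DLT (Sections 5.4.2 and 13.4.1).
- 100 mg start, Cohort A: 12 patients planned (13.4.1). With the first 3 this gives 15, the response-evaluable size in 13.2. Replacement of inevaluable patients could make the toxicity denominator larger; 15 is used here.
- DLT rule: the dose level passes if fewer than 3 of 12 patients have a cycle 1 DLT; null 39%, alternative 9%; stated power 91.3% and type 1 error 9.5% (13.4.1).
- DLTs observed at 100 mg: not in the documents. The passing range 0 to 2 of 12 is assumed.

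**Step 1. Reproduce the plan's figure.** For X binomial with n = 12:
- P(X ≤ 2 | p = 0.09) = 0.9134, against a stated 91.3%.
- P(X ≤ 2 | p = 0.39) = 0.0946, against a stated 9.5%.

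Both agree to the stated rounding. The rule is a correctly computed assessment of the lower dose alone.

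**Step 2. What a mixed table does in general.** With r125 and r100 the proportions in the two groups,

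pooled = (3 × r125 + 12 × r100) / 15 = 0.2 × r125 + 0.8 × r100.

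The displayed figure therefore differs from r100 by 0.2 × (r125 − r100). For any single toxicity the shift cannot exceed 20 percentage points (3/3 against 0/12). Its direction depends on which group has the higher rate.

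**Step 3. Illustration with cycle 1 DLTs**, the only event with a count at 125 mg in the documents: 2/3 = 66.7% (exact 95% CI 9.4 to 99.2%).

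| Assumed DLTs at 100 mg | By starting dose (exact 95% CI) | Pooled over 15 (exact 95% CI) | Difference |
|---|---|---|---|
| 0/12 | 0% (0 to 26.5%) | 2/15 = 13.3% (1.7 to 40.5%) | 13.3 points |
| 1/12 | 8.3% (0.2 to 38.5%) | 3/15 = 20.0% (4.3 to 48.1%) | 11.7 points |
| 2/12 | 16.7% (2.1 to 48.4%) | 4/15 = 26.7% (7.8 to 55.1%) | 10.0 points |

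If the true 100 mg rate were the alternative value of 9%, the expected pooled proportion would be (2 + 12 × 0.09) / 15 = 20.5%.

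**Step 4. What the DLT rule leaves uncovered.** Set beside 13.3.3, the rule in 13.4.1:
- uses first-cycle DLTs only (5.4.1), while treatment may run to 12 cycles (5.1.1);
- compares a count with a threshold and plans no estimate or interval;
- treats patients with marrow metastatic disease at entry as not evaluable for hematologic DLT (5.4.1).

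Non-DLT events, cycles after the first, and hematologic toxicity in marrow-involved patients thus have no planned summary by dose.

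**The case against.** A reader might infer that the toxicity objective goes unanswered for the 100 mg start. The documents do not support that. Section 13.4.1 sets the first 3 patients aside, applies its rule to the 12 lower-dose patients only, and ends in a conclusion about that dose level. Section 5.4.2 restarts the count after any contingency dose. The safety outcome that drives decisions is already separated by dose.

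It follows that the table in the working measures something the plan does not schedule, since no section calls for a DLT proportion over all 15 patients. This is correct, and the figures stand only as an illustration of how far mixing 3 with 12 can move a rate.

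Objective 1.2.2 asks for a description of the combination's toxicity in each disease cohort, not for a rate at a named dose, so by-cohort tables meet its wording. That is also true, but a primary description that cannot be read by dose, after a change of dose made for toxicity, is less useful than it could be at almost no cost.

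Finally, starting dose is not actual dose after cycle 1. Patients who resume after a DLT generally do so at a reduced dose (6.1, 6.2, 6.5), and a 125 mg column holds at most 3 patients. Both limits stand. They call for flagging and for caution in reading the tables, and do not favor leaving the two starts mixed.

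**Conclusion.** The point holds in limited form. As written, the descriptive toxicity tables for Cohort A combine 3 patients started at 125 mg with about 12 started at 100 mg. The gap covers toxicities other than cycle 1 DLTs, later cycles, and the absence of a by-dose DLT proportion with an interval.

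For cycle 1 DLTs, pooling would raise the displayed proportion by 10 to 13 percentage points, on the assumptions of 0 to 2 DLTs among 12 at 100 mg and a denominator of 15. The intervals overlap widely.

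Two stronger readings are not supported:
- That the plan instructs pooling of toxicity across doses. The pooling sentence in 13.3.1 is confined to efficacy, and the mixing of toxicity arises by omission.
- That early hematologic or other toxicity would be inflated in the same way. The statistical and dosing sections do not say which toxicities the two DLTs were and give no other event counts for the 125 mg starters, so neither size nor direction can be shown.

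This is a worthwhile reporting correction for a primary objective. It is not a flaw in the monitoring rule or in the trial's error rates.

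**What to change.** In 13.3.3, and in the matching tabulation sentences of 13.4 and 13.4.2:
- Tabulate toxicity by cohort, by starting dose level (including any later contingency level) and by cycle, keeping type, severity and attribution.
- Report the first-cycle DLT proportion with an exact 95% CI for each starting dose, and state the evaluable denominator.
- State that cells based on 3 patients are descriptive only.
- State that cycles given after a dose reduction are shown under the starting dose and flagged as reduced.

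Leave the pooled primary response analysis in 13.3.1 unchanged; a breakdown of responders by starting dose is not needed for this point.

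The cost is a few sentences and an extra table column. Starting dose is known for each patient, so no new data or patients are needed. Sample size, error rates, dosing and stopping rules do not change. The price is sparse cells, and a starting-dose label that may not match the dose received after cycle 1. Fixing the layout in advance also removes a later choice about which patients the safety table shows.
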